4.10 Subject Withdrawal

A study subject has the right to discontinue participation at any time without penalty or loss of benefits to which the subject is otherwise entitled. A withdrawn subject will be treated according to standard of medical care and will not be replaced.

5.0 BENEFITS AND RISKS

5.1 Benefits

There are no guaranteed benefits from participation in this study. Participation in the study offers another dermatological approach to accomplish the same clinical effect as the typical surgical devices currently used to treat patients with SH lesions. The information learned from this study may contribute to the ultimate use of a safer and more effective device and the availability of the device to treat benign and non-benign lesions as an alternative for use in future patients.

5.2 Risks

For detailed information on the risks of the devices used in the study procedure, including a complete list of warnings, precautions, and potential adverse events, please refer to the Instructions for Use (IFU) for the Pulse Bioscience CellFX® System.

5.3 Mitigation of Risks

As with any dermatological procedure, appropriate safety precautions will be followed. Risks observed or theoretical adverse events have been mitigated through the Instructions for Use, physician training, and patient selection in the study protocol.

All efforts will be made to minimize these risks by:

- Site Selection
- Patient Population that represents the demographics of the U.S with a uniform distribution of Fitzpatrick Skin Types I, II, and III
- Ensuring compliance to the protocol and IFU
- Study monitoring
- Safety processes-protocol adverse events reporting requirements

6.0 STATISTICAL CONSIDERATIONS

Further details of planned analyses can be found in the statistical analysis plan (SAP).

6.1 Co-Primary Endpoints

Clinical acceptance of treatment with the CellFX System for SH lesions requires both non-inferior improvement in lesion appearance (effectiveness) and non-inferior rates of adverse skin changes (safety) versus Electrodesiccation. Because both features are critically important for treatment acceptability, this study is designed with 3 co-primary endpoints (1 related to appearance and 2 related to adverse skin changes). All 3 endpoints must demonstrate non-inferiority be considered successful.¹⁹ These co-primary endpoints are: (1) rate of pigmentary changes and scarring at 60 days post last treatment, (2) rate of skin textural changes at 30 days post last treatment and (3) rate of improvement in aesthetic appearance. All 3 co-primary endpoints are assessed at a lesion level, but the analyses will be adjusted for within-subject correlation. The pigmentary changes and scarring primary safety endpoint is the proportion of lesions with the presence of hyperpigmentation, hypopigmentation or scarring at 60 days post last treatment. The skin textural change primary safety endpoint is the proportion of lesions with the presence of crusting, flaking, or other skin textural change. The primary effectiveness endpoint is the proportion of lesions classified as responders on the Global Aesthetic Improvement Scale (GAIS).²²

6.1.1 Primary Safety Endpoints

The first primary safety endpoint is the presence or absence of hyperpigmentation, hypopigmentation or scarring at 60 days from the last CellFX or Electrodesiccation treatment as assessed by the blinded site investigator. The timing of the evaluation of this endpoint is lesion specific as some lesions may not require a second treatment with the CellFX System or Electrodesiccation. Lesions will be categorized as having this safety event if any component (hyperpigmentation, hypopigmentation, or scarring) is present at the follow-up visit 60 days after the last treatment.

Clinical justifications for the 15% non-inferiority margin for the primary safety endpoints include the avoidance of electrosurgical smoke plume, which may be harmful to patients and providers,²⁰ as well as existing safety data that demonstrate no serious adverse events. Safety data show a comparable safety profile for CellFX compared to the predicate devices for this indication, with the suggestion of faster healing.

The statistical hypotheses to be evaluated for the pigmentation and scarring primary safety endpoints are:

$$\begin{aligned} H_0: p_{CellFX} - p_{Electro} &\geq 15\% \text{ at 60 days post last treatment, versus} \\ H_A: p_{CellFX} - p_{Electro} &< 15\% \text{ at 60 days post-last treatment} \end{aligned}$$

Where p_{CellFX} and $p_{Electro}$ are the proportion of lesions with any of these events (hyperpigmentation, hypopigmentation, or scarring) in each treatment group. The null hypothesis will be rejected if the upper bound of the 2-sided 95% confidence interval for the absolute difference in proportions ($p_{CellFX} - p_{Electro}$) is less than 15%. This approach is equivalent to a 1-sided test with a 2.5% type I error rate. To be clinically meaningful, the absolute difference should not exceed 7.5%.

This second safety endpoint is the presence or absence of skin textural changes (scaling, flaking etc.) at 30 days from the last CellFX or electrodesiccation treatment as assessed by the blinded site investigator. The timing of the evaluation of this endpoint is lesion specific as some lesions

may not require a second treatment with the CellFX System or electrodesiccation. Lesions will be categorized as having this safety event if any skin textural change is present at the follow-up visit 30 days after the last treatment.

The statistical hypotheses to be evaluated for the skin texture change primary safety endpoint are:

$$H_0: p_{CellFX} - p_{Electro} \geq 15\% \text{ at 30 days post last treatment, versus}$$

$$H_A: p_{CellFX} - p_{Electro} < 15\% \text{ at 30 days post-last treatment}$$

Where p_{CellFX} and $p_{Electro}$ are the proportion of lesions with scaling, flaking or other skin textural changes in each treatment group. The null hypothesis will be rejected if the upper bound of the 2-sided 95% confidence interval for the absolute difference in proportions ($p_{CellFX} - p_{Electro}$) is less than 15%. This approach is equivalent to a 1-sided test with a 2.5% type I error rate. To be clinically meaningful, the absolute difference should not exceed 7.5%.

Because multiple lesions are treated within subjects, the difference in proportion and 95% confidence interval will be calculated using generalized estimating equations (GEE).²¹ The dependent variable is the presence or absence of a safety event for each lesion at 60 days post last treatment, with randomized treatment strategy included as a fixed effect. A repeated term for subject will be included to account for the within-subject correlation. An exchangeable working correlation matrix will be used to reflect a common correlation across lesions within subject.

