4.5.3 CellFX Treatment / Electrodesiccation Treatment

- Up to 10 clinically diagnosed SH lesions that meet the study criteria will be selected by the treating investigator and prior to assigning lesions the subjects should have baseline photos taken.
- The site will log onto the Captivate EDC system. The randomization assignment will include the type of treatment and which side of the face for CellFX and Electrodesiccation.
- A template may be used to determine which treatment tip size will be used for each lesion – sizes range between 1.5 mm x 1.5 mm and 5.0 mm x 5.0 mm. The identified lesions will be numerically labeled.
- The blinded site investigator will then perform a baseline lesion(s) assessment.
- Photographic images of each selected lesion will be taken prior to using local anesthesia/numbing.
- Local anesthesia/numbing will be applied to all selected study lesions.
- Each lesion randomized to CellFX will be treated with pre-determined energy settings; each lesion randomized to Electrodesiccation will be treated as defined in **Section 3.5**.
- The subject will be asked to rate his/her pain immediately after each lesion treated with the CellFX and Electrodesiccation procedures by using a numerical rating score.
- The subjects will be asked whether they felt muscle twitching immediately after each lesion treated with CellFX.
- Post procedure lesion assessment will be performed by the blinded site investigator.
- Photographic images of each selected lesion will also be taken post-treatment.
- A light bandage and/or any physician recommended dressing may be applied before the subject leaves the clinic.
- Any adverse events will be identified and documented.

4.6. 7-Day Follow-up Visit

- Photographic images of each of the study lesions will be taken with pre and post lesion markings.
- All lesions will be clinically assessed by the blinded site investigator.
- Any adverse events will be identified and documented.

4.7 30-Day Follow-up Visit (Optional CellFX/Electrodesiccation Treatment #2)

- Photographic images of each of the study lesions will be taken with pre- and postlesion markings.
- All lesions will be clinically assessed by the blinded site investigator and rated using GAIS scale and the 4-point lesion clearance scale.
- If any lesion is rated 1-4 on the GAIS scale, a second treatment with CellFX or electrodesiccation will be performed to the previously treated lesion.

In case of a second CellFX or Electrodesiccation treatment:

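### The pigment and scarring co-primary is framed as skin changes but scored as any mark present at 60 days, so a Day 0-referenced analysis should be prespecified beside it

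*Combined protocol and SAP*

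**What the plan says.** Protocol section 6.1 states the safety aim as "non-inferior rates of adverse skin changes (safety) versus Electrodesiccation" and names the first co-primary the "rate of pigmentary changes and scarring at 60 days post last treatment". The same section then defines it as "the proportion of lesions with the presence of hyperpigmentation, hypopigmentation or scarring at 60 days post last treatment". Section 6.1.1 gives the scoring rule: "Lesions will be categorized as having this safety event if any component (hyperpigmentation, hypopigmentation, or scarring) is present at the follow-up visit" at 60 days. The GEE paragraph of 6.1.1 adds "The dependent variable is the presence or absence of a safety event for each lesion at 60 days post last treatment", with treatment as the only fixed effect. Neither section asks whether the mark was there before treatment.

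Lesion eligibility in 4.2.1 covers size and location. The scar criterion in 4.2.2 concerns subjects prone to hypertrophic scars or keloids, not lesions already marked. The only exclusion for earlier treatment of these lesions is prior CellFX, and 6.5 lists previous treatment of study lesions as a subgroup.

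Some pre-treatment information exists. Section 3.2 has the blinded investigator classify healing characteristics at baseline, Table 2 ticks wound healing at Visit 1, and 4.5.3 says "The blinded site investigator will then perform a baseline lesion(s) assessment", before anaesthesia. It also says "prior to assigning lesions the subjects should have baseline photos taken". Section 6.0 adds "Further details of planned analyses can be found in the statistical analysis plan (SAP"; no separate SAP text is among the documents reviewed.

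**The concern.** A change is a comparison with an earlier state, and the scoring rule makes none. A pigment spot or scar left by an earlier procedure, if still visible at day 60, is counted against whichever device treated that side. The background sections describe pigment change and scarring after several of the older methods, and lesions treated by those methods may enter.

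Randomising the side of the face balances such marks in expectation, so they do not push the estimate toward one device. They do dilute: lesions that are positive whatever the treatment does cannot show a difference. In a non-inferiority test of harm, dilution makes a real CellFX excess look smaller. At stake is what a pass would say about new harm to the skin. The effectiveness co-primary (6.1.2) avoids the difficulty because it is rated against baseline photographs.

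**Working it through.** **The plan's own figure.** Section 6.3 gives 240 lesions for at least 80% power, from a bootstrap of SH-009 data that are not in the documents, so it cannot be reproduced. A closed-form check on the 73% GAIS response rate (equal arms, 15-point margin, 120 lesions per arm) gives 74.4% power with independent lesions and 80.1% with within-subject correlation 0.13. The stated figure is therefore plausible. The safety event rates used in the bootstrap are not given.

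**Inputs.** From the documents: margin 15 points; two-sided 95% interval (6.1.1); 240 or 260 lesions (6.3), so n = 120 or 130 per arm. Assumed: new-event rates of 30% (CellFX) and 15% (electrodesiccation), a true excess exactly at the margin; within-subject correlation ρ = 0 or 0.25; persisting share a = 0–10%. Here a is the share of lesions whose Day 0 mark is still present at day 60, equal on both sides. It is not Day 0 prevalence.

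**Formulas.** Presence rate = a + (1−a)p. Observed difference = (1−a)(p_C − p_E). Margin on the new-event scale = 15/(1−a). SE = √{[p_C(1−p_C) + p_E(1−p_E)]/n × (1−ρ)}, using presence rates. Probability of declaring non-inferiority = Φ[(0.15 − observed difference)/SE − 1.96].

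**Worked case, a = 5%, n = 130, ρ = 0.** CellFX 0.05 + 0.95 × 0.30 = 0.335; electrodesiccation 0.05 + 0.95 × 0.15 = 0.1925; difference 0.1425; SE 0.0539. Φ(0.0075/0.0539 − 1.96) = Φ(−1.82) = 3.4%.

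| a | observed difference (points) | effective margin (points) | error for new events |
|---|---|---|---|
| 0 | 15.0 | 15.0 | 2.5% |
| 2% | 14.7 | 15.3 | 2.8–2.9% |
| 5% | 14.25 | 15.8 | 3.4–3.6% |
| 10% | 13.5 | 16.7 | 4.4–4.9% |

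Ranges cover n = 120–130 and ρ = 0–0.25. With comparator rates of 5–20%, the error at a = 5% is 3.3–3.8%.

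**Marks that clear.** If 5% of lesions are marked at Day 0 and half the marks clear on both sides, a = 2.5% and the error is 2.9–3.0%.

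**Unequal persistence, 5% marked at Day 0.** If half the marks clear on the electrodesiccation side only, the error is 1.2–1.4%. If half clear on the CellFX side only, it is 6.5–7.8%, part of which is real benefit. Section 1.5 reports CellFX effects on melanocytes, so unequal persistence is possible.

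**Simulation.** With 52 subjects, 2 or 3 lesions per side and a subject-level robust variance, presence scoring gives 2.8–3.2% at a = 0, about 3.9–4.2% at 5% and 4.8–5.4% at 10%. Restricting to lesions unmarked at Day 0 gives 2.8–3.3% at both 5% and 10%, which is the test's own small-sample level.

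**New-or-worse scoring in all lesions.** If a marked lesion gains a countable event half as often as an unmarked one (assumed), the observed difference at a = 10% is (0.90 + 0.10 × 0.5) × 15 = 14.25 points and the closed-form error is 3.5–3.7%. This reduces the dilution without removing it.

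**Power at a = 10%, equal arms, 10% new-event rate.** Restricted set (n × 0.9): 96–99%. Presence scoring in all lesions (rate 0.10 + 0.90 × 0.10 = 19%): 84–95%.

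**The case against.** The strongest reply is that no stated hypothesis loses error control. The hypotheses in 6.1.1 concern presence at 60 days, and the definition in 6.1 is explicit whatever the endpoint is called. That stands. A reader might infer from the table that the trial's type I error is inflated; it is not. The percentages above 2.5% belong to a new-event hypothesis that the plan does not state. All three co-primaries must also pass, so they are upper bounds on false study success by this route.

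The size rests on an unknown. No document gives a, and the 0–10% range is mine. At a = 2% the excess over 2.5% is no larger than the small-sample error of the test itself. This stands too, and it limits the claim.

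A reader might infer that the baseline data are certainly in hand. The documents suggest this but do not show it. The Day 0 assessment is not itemised, the Visit 1 tick may refer to the post-procedure assessment, section 6.2 lists the wound-healing items only at 7, 30 and 60 days, and the case report form is a separate attachment.

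A reader might also conclude that the primary population should be replaced by lesions unmarked at Day 0. That goes too far. It would drop a pigmented lesion that later scars, and it would narrow the modified-ITT safety set of 6.4 using an assessment that 4.5.3 lists after randomisation. Nor is a power shortfall supported, since the SH-009 bootstrap may already include such marks. Finally, the separate SAP may hold a baseline rule, so a definite omission cannot be asserted.

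What survives is the gap between aim and scoring within 6.1 and 6.1.1.

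**Conclusion.** The point holds in limited form. As written, 6.1.1 counts an old, persisting mark as a safety event while 6.1 speaks of changes, and the protocol admits lesions on which this can happen. The presence test is valid at 2.5%. As evidence on new events, the 15-point margin acts as 15.3 to 16.7 points for a persisting share of 2–10%, with single-endpoint error of about 2.8% to 4.9% at a true 15-point excess. These figures assume equal persistence on both sides, 30% versus 15% new events, 120–130 lesions per arm and ρ of 0–0.25. The effect is negligible if few marks persist, and its direction is unknown if persistence differs by arm. The gap in definition is clear from the text; confidence in the size of the effect is low to medium. Importance lies between worth considering and should be done, mainly because the remedy is cheap and must be set before unblinding to be credible.

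**What to change.** In 6.1.1, keep any-presence in all modified-ITT lesions as the primary analysis. Before unblinding, prespecify a Day 0-referenced analysis with the same GEE and 15% margin, in two forms:

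- (i) Lesions free of all three components at the blinded Day 0 assessment.
- (ii) All modified-ITT lesions, counting for each component a finding that is new since Day 0 (or worse, if the form grades it), so that a new scar in an already pigmented lesion still counts.

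The two complement each other: (i) removes the dilution but loses lesions, and (ii) keeps every lesion but may retain some dilution. Do not score marked lesions as automatic non-events; at a = 10% that rule gives 4.8–5.4% error. Report Day 0 prevalence by treated side. State that a conclusion about treatment-caused skin changes requires the Day 0-referenced result to agree with the presence result.

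First confirm that the case report form records hyperpigmentation, hypopigmentation and scarring before treatment. If it does not, score them from the baseline photographs. Those photographs, taken before lesions are assigned, also provide a check on the blinded assessment. Reconcile the wording with any baseline rule in the separate SAP.

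Cost: a wording change, a little more derivation and analysis, and a check of the form. At 2, 5 or 10% Day 0 prevalence, about 5, 13 or 26 of 260 lesions leave analysis (i). In the simulation an average of 0.1–1.0 of 52 subjects at 5%, or 0.6–2.6 at 10%, lose one side of the pairing, depending on how far marks cluster within subjects. The primary analysis and its population do not change.

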6.1.2 Primary Effectiveness Endpoint

The primary effectiveness endpoint is response measured by the Global Aesthetic Improvement Scale (GAIS) at 60 days following the last CellFX or Electrodesiccation treatment (60 days post-last treatment). GAIS score will be assessed by three independent observers, blinded to treatment assignment, who will classify the response for each lesion based on photographs taken at baseline and 60 days post last treatment. The 3 observers will assign a score based on the 5-level GAIS scale described in this section. For analysis purposes, the lesion will be classified as a responder if 2/3 blinded observers assign a score of 4 or 5, and as a non-responder if 2/3 blinded observers assign a score of 1, 2 or 3. The timing of the evaluation of this endpoint is lesion specific as some lesions may not require a second treatment with the CellFX System or Electrodesiccation. The GAIS scale²² describes aesthetic changes as follows:

GAIS Rating	Description
5=Much Improved	Marked improvement in appearance from the initial condition, touch-up treatment(s) is not indicated
4=Improved	Obvious improvement in appearance from the initial condition, but a touch-up or re-treatment is indicated
3=No Change	The appearance is essentially the same as the original condition
2=Worse	The appearance is worse than the original condition
1=Much Worse	The appearance is much worse than the original condition

The primary effectiveness endpoint is lesion-level GAIS response, defined as a score of 5 ("Much Improved") or 4 ("Improved") versus non-response defined as a score of 3, 2 or 1 ("No Change", "Worse", "Much Worse") for at least 2/3 blinded observers. This dichotomization of the GAIS scale has been used to define response in several previous cosmetic procedures.²³⁻²⁶

The 15% non-inferiority margin for the primary effectiveness endpoint is justified by consistency of treatment and ease of use with the CellFX system. Outcomes for standard of care Electrodesiccation procedures depend heavily upon operator skill and experience. Furthermore, electrodesiccation involves destruction of the entire gland but can lead to sequelae such as scarring and discoloration. Therefore, depending on the number of lesions and the cosmetic concerns of the patient, it may be necessary to avoid such interventions.²⁷ In contrast, the CellFX system is designed to be a straightforward procedure that is reproducible among providers with fewer sequelae.

The statistical hypotheses to be evaluated for the primary efficacy endpoint are:

$$H_0: p_{CellFX} - p_{Electro} \leq -15\% \text{ at 60 days post last treatment, versus}$$

$$H_A: p_{CellFX} - p_{Electro} > -15\% \text{ at 60 days post last treatment}$$

Where p_{CellFX} and $p_{Electro}$ are the proportion of lesions with a GAIS response (“Much Improved” or “Improved”) in each treatment group. The null hypothesis will be rejected if the lower bound of the 2-sided 95% confidence interval for the absolute difference in proportions ($p_{CellFX} - p_{Electro}$) is greater than -15%, which is equivalent to a 1-sided test with a 2.5% type I error rate.

Because multiple lesions are treated within subjects, the 95% confidence interval will be calculated using GEE.²¹ The dependent variable is GAIS response each lesion at 60 days post last treatment, and randomized treatment strategy will be included as a fixed effect. A repeated term for subject will be included to account for the within-subject correlation. An exchangeable working correlation matrix will be used to reflect a common correlation across lesions within subject.

6.1.3 Type I Error Control and Study Success

Study success requires the demonstration of non-inferiority for the primary safety and efficacy endpoints.¹⁹ Thus, no type I error adjustment for multiple testing is required. No formal hypothesis will be tested for secondary endpoints. In addition, the point estimate for the response rate for the primary effectiveness endpoint among lesions treated with CellFX must be greater than 60%.

6.2 Secondary Endpoints

Details of the planned analyses for secondary endpoints can be found in the statistical analysis plan. No formal hypotheses will be tested for secondary endpoints. Secondary endpoints collected in this study are as follows:

1. The investigator, blinded to treatment assignment, will classify the aesthetic change for each lesion using photographs taken at baseline as a reminder of baseline condition. The score will be assigned based on the in-person observation at 60 days post last treatment according to the GAIS scale²². A GEE model similar to the model described in **Section 6.1.2** will be performed to assess differences in the investigator-assess response rate.
2. Difference in proportion with GAIS improvement between CellFX and Electrodesiccation based on score assigned by blinded site investigators from baseline to 30-days post-last treatment.
3. Wound healing characteristics at 7-days, 30-days, and 60-days post-last treatment between CellFX and Electrodesiccation. Wound healing includes evaluation of the following:
 - Hyperpigmentation
 - Hypopigmentation

- Erythema
- Crusting
- Scabbing
- Flaking
- Scarring
- Other surface irregularities

The rate of each event individually and a composite of any of these events will be calculated for each treatment and time-point. Differences in proportion and 95% confidence interval as described for the hyperpigmentation, hypopigmentation or scarring endpoints will be calculated using GEE, convergence permitting.

4. The **GAIS Scale** will be used to measure aesthetic improvement for each treated lesion site (left, right).²³⁻²⁶

The proportion with each response will be summarized. An analysis will be performed using the same response definition as for the primary efficacy outcome (see **Section 6.1.2**) to compare investigator and subject perception of change across treatment groups.

5. A **6-point Subject Satisfaction Scale** will be used to measure subject's satisfaction with the overall treatment of their SH lesions by treated lesion site (left, right):

Rating	Description
6	Very Satisfied
5	Satisfied
4	Somewhat Satisfied
3	Somewhat Dissatisfied
2	Dissatisfied
1	Very Dissatisfied

The proportion with each response will be summarized. An analysis will be performed using the binary endpoints of satisfied ("Very Satisfied" or "Satisfied") versus not satisfied ("Somewhat Satisfied", "Somewhat Dissatisfied", "Dissatisfied", "Very Dissatisfied") to compare satisfaction across treatment groups.

6. A **5-point Recommendation Scale** will be used to measure the subject's likelihood of recommending the treatment procedure used on each treated lesion site (left, right) to a significant other, relative or friend.

[figure not shown]
Rating	Description
5	Highly Likely
4	Likely
3	Neutral
2	Unlikely
1	Highly Unlikely

The frequency of each response will be tabulated by treatment. The proportion with responses of "Highly Likely" or "Likely" will be tabulated and compared across treatments.

7. **Face Pain Scale** with an assigned numerical rating between 0 (smiling) and 10 (crying) will be

used to assess pain immediately after the CellFX and Electrodesiccation treatments at Day 0 and 30 days, if applicable. The face pain scale will be assessed immediately after each lesion treatment (left, right). Please see pain scale chart below.

The number and percent will be tabulated for each level of pain for first and second treatments separately, and GEE models using score as a continuous dependent variable and treatment as a fixed covariate (adjusted for within-subject correlation) will be used to compare the least-square mean difference in pain scores across treatment groups.

